2.3.2.2 Freedom from biochemical failure

2.3.2.3 Freedom from local failure

2.3.2.4 Freedom from elsewhere prostate failure

2.3.2.5 Freedom from regional failure

2.3.2.6 Freedom from distant metastasis

2.3.2.7 Freedom from hormone therapy

2.3.2.8 Disease-free survival.

2.3.2.9 Disease-specific survival

2.3.2.10 Overall Survival.

- 2.3.2.11 Patient reported Health-related quality of life as measured by the IPSS and EPIC-26 assessments (see Appendices B and C).
- 2.3.3 NCI CTCAE v4.03 toxicity criteria will be used to assess acute and late adverse events/toxicity endpoints (Appendix A). Disease specific endpoints will utilize a combination of laboratory values, multidisciplinary clinical decisions, radiographic imaging, functional imaging, and initiation of salvage therapy.

3.0 PATIENT ELIGIBILITY

Eligibility waivers are not permitted. Subjects must meet all of the inclusion and exclusion criteria to be registered to the study. Study treatment may not begin until a subject is registered.

3.1 *Inclusion Criteria*

- 3.1.1 Biopsy proven locally recurrent adenocarcinoma of the prostate after the completion of definitive radiation therapy for initially diagnosed prostate cancer.
 - 3.1.1.1 Biopsy must be performed within 182 days of trial registration
 - 3.1.1.2 Biopsy should be at least a standard sextant TRUS-guided biopsy
- 3.1.2 Initial cancer diagnosis that fits these specific criteria:
 - 3.1.2.1 Stages cT1-T3a
 - 3.1.2.2 Nx or N0
 - 3.1.2.3 Mx or M0
- 3.1.3 Eligible initial definitive radiotherapy modalities include:
 - 3.1.3.1 External beam radiotherapy, with photon or proton beam therapy
 - 3.1.3.11 Conventional or moderately hypofractionated radiotherapy
 - 3.1.3.12 Extremely hypofractionated external beam radiotherapy (Stereotactic body radiation therapy)
 - 3.1.3.13 Treatment of the pelvic nodes with prior course of radiotherapy is not allowed.**

3.1.3.14 No prior radiotherapy to the intended target for this course of radiotherapy other than prostate radiotherapy

3.1.3.2 Definitive Brachytherapy:

- 3.1.3.21 Low-dose rate
- 3.1.3.22 High-dose rate
- 3.1.3.23 Combined EBRT and brachytherapy
- 3.1.3.24 Treatment of the pelvic nodes with prior supplemental EBRT is not allowed.

3.1.4 Fluciclovine-positive pelvic nodes (as determined by an interpreting radiologist or nuclear medicine physician) in the pelvic nodal region (defined as the pelvic nodal regions up to the common iliac nodal region) without any evidence of lymph node involvement outside of this area or distant metastases

3.1.4.1 This will be based on the following imaging workup:

- 3.1.4.11 CT A/P or MRI Pelvis**
- 3.1.4.12 Bone scan**
- 3.1.4.13 Fluciclovine PET/CT**

3.1.5 Candidate for hormonal therapy.

3.1.6 Current ECOG Performance status Scale 0-2 (Appendix D)

3.1.7 Current International Prostate Symptom Score (IPSS) < 20 (Appendix B)

3.1.8 Age ≥ 18

3.1.9 The patient must be medically suitable to receive general or spinal anesthesia.

3.1.10 AST, ALT, and alkaline phosphatase < 2 x upper institutional limit within 3 months of registration.

3.1.11 The patient must be able and willing to sign a study-specific written informed consent form before study entry.

3.2 *Exclusion Criteria*

- 3.2.1 Preregistration GI or GU toxicity (for any reason) grade ≥ 3 as defined in CTCAE version 4.03. That is, grade ≥ 3 GU or GI toxicity after first course of radiotherapy
- 3.2.2 Treatment to a “whole pelvis” field with initial radiotherapy
- 3.2.3 Prior radiotherapy to the region of the body that is intended to be the target with the current course of RT.
- 3.2.4 Patients with distant metastases (such as to the bone, visceral organs, and lymph nodes other than the pelvic nodes including the common iliac nodes).
- 3.2.5 Patients receiving any other investigational agents.
- 3.2.6 Uncontrolled inter-current illness including, but not limited to, ongoing or active infection, severely symptomatic congestive heart failure, cardiac arrhythmia, recent myocardial infarction in last 6 months, or psychiatric illness/social situations that could limit compliance with study requirements.
- 3.2.7 Patients who have received chemotherapy or immunotherapy within one month prior to study enrollment, other than ADT.

4.0 PRETREATMENT EVALUATIONS/MANAGEMENT

4.1 *Additional Mandatory Pretreatment Evaluations/Interventions*

- 4.1.1 Documentation of pharmacologic agents used by patient to treat urinary, bowel or erectile dysfunction.
- 4.1.2 Baseline Quality Of Life assessments, including IPSS, EPIC-26 assessments (Appendices B and C)
- 4.1.3 Eastern Cooperative Oncology Group (ECOG) performance assessment (Appendix D)
- 4.1.4 Any preoperative assessments needed for the brachytherapy implant operative procedure
- 4.1.5 AST, ALT, and alkaline phosphatase $< 2 \times$ upper institutional limit within 3 months of registration.

5.0 REGISTRATION PROCEDURES

Patients may not begin protocol treatment prior to registration. All patient registration will be centralized through the Department of Radiation Oncology Research Office. All

eligibility criteria must be met in order for a patient to be registered. To register a patient call [contact], Monday-Friday 9:00am-5:00pm

5.1 *Access to Registration*

The Department of Radiation Oncology Research Office Study Coordinator, [name], will coordinate all patient registrations. For any questions regarding patient registration please call: [contact].

5.2 *Registering a Participant*

Obtain and file participant's signed and witnessed informed consent document in the Radiation Oncology Research Office.

5.3 *Other Relevant Clinical Trials*

At Loyola University Medical Center, there are no other clinical trials that will affect enrollment into this study, and this study will not affect enrollment into other clinical trials available at the institution.

6.0 RADIATION THERAPY

RT will start ~2 months after the start of ADT when possible (with RT starting earlier or later based on physician discretion). Either Brachytherapy or EBRT can be delivered first, or brachytherapy can be intercalated with EBRT course based on treating physician discretion.

6.1 *Brachytherapy Implant procedure:*

6.1.1 Patients will undergo 2 implants with 1 fraction of 12 Gy delivered with each implant, scheduled 1-2 weeks apart when possible, although longer or shorter intervals are acceptable with PI approval.

6.1.2 The implant procedure will be done under general anesthesia. The patient should be placed in the lithotomy position, generally after appropriate anesthesia. Then the perineum will be prepped and draped. A Foley catheter should be inserted for better visualization of the urethra and the bladder for the duration of the implant. Then, a single fiducial marker should be placed in the area of the target lesion as close to the lesion center as possible. Then, the brachytherapy loading catheters should be placed with the aid of a Liberty Medical template to allow for at least adequate coverage of the target lesion. Once adequate placement is confirmed by transrectal ultrasound (TRUS), the template will be sutured to the perineum. The patient's legs should be returned to a neutral position. After the patient is awoken from anesthesia and has stabilized, he will then be transferred to the Radiation Oncology Department for CT simulation, treatment planning, and radiation delivery.

- 6.1.3 Patient controlled analgesia (PCA), IV, or PO pain medications may be used during the post-operative period for pain control and throughout the day of the procedure as needed.
- 6.1.4 After completion of each of the brachytherapy treatments (upon completion of MRI and Treatment planning), all catheters should be removed.

6.2 Brachytherapy Treatment Planning

- 6.2.1 CT Simulation: CT simulation will be performed per standard protocol for evaluation of catheter position and treatment planning.
- 6.2.2 Diagnostic MRI: When possible, patient will undergo a diagnostic MRI after the implant with the catheters in position to aid in treatment planning. This will be registered to the CT image set.
- 6.2.3 Volume delineation: Target volumes and organs at risk (OARs) will be contoured using brachytherapy planning software. The patient's prior multi-parametric MRI and the fiducial placed during the procedure can be used to help define the target.
- 6.2.4 Source Loading: The HDR treatment will be delivered on the day of the catheter placement, after visual inspection of the catheters prior to delivery of the treatment is performed, and any necessary catheter adjustments are made prior to the treatment. If the catheters cannot be satisfactorily repositioned and cannot be corrected by a new plan with appropriate coverage of the target and sparing of the OARs, then we will consider postponing or aborting the treatment

6.3 Brachytherapy Volume Delineation:

- 6.3.1 Target Volume: The target volume will consist of the prostate and proximal seminal vesicles encompassing the area of local recurrence. The Planning Target Volume (PTV) will be defined as the GTV, plus a 0-5 mm margin, restricted to adjacent OARs applicable.
- 6.3.2 Critical Structures: Critical structures to be contoured include the bladder, Foley bulb, rectum, and urethra. Critical structures must be contoured on every CT slice that contains a target volume and in at least 3 slices (9 mm) above and below the CTV

6.4 Brachytherapy Dose Specifications:

- 6.4.1 For each brachytherapy procedure, the prescription dose to the PTV and GTV will be the highest deliverable dose up to 12 Gy in one fraction. Priority will be given to the normal tissue dose constraints over the

prescription dose. That is, the maximum dose will be that which is achievable without violating the normal tissue dose constraints. Priority will be given to GTV coverage first and then CTV coverage. If necessary, treatment to areas of the prostate/seminal vesicles judged to be at low risk of involvement can be omitted if it is felt that delivering full dose to these areas would result in unacceptable significant risk of toxicity.

In general, the volume of the GTV getting 100% of the prescription dose should be $\geq 95\%$ when possible ($V100 \geq 95\%$) and, again, when possible, prescription dose should be delivered to at least 90% of the GTV ($D90 \geq 100\%$). The same coverage goals apply to the PTV, although this is less of a priority and can also be a lower dose than that prescribed to the GTV due to normal tissue constraints.

The normal tissue dose constraints will be as follows:

Bladder: $D \text{ 0.1 cc} \leq 95\%$

$D \text{ 1 cc} \leq 75\%$

$V75\% \leq 1 \text{ cc}$

Foley Bulb: $D \text{ 0.1 cc} \leq 80\%$

Rectum: $D \text{ 1 cc} \leq 75\%$

$V75\% \leq 1 \text{ cc}$

Urethra: Max point dose $\leq 120\%$

$D \text{ 1 cc} \leq 110\%$

6.5 External Beam Radiotherapy Treatment Planning

- 6.5.1 Patients will undergo CT simulation prior to treatment planning.
- 6.5.2 The GTV will be any nodes in the pelvis (up to the common iliac nodes) felt by the treating physician to be involved with the cancer based on radiographic, pathologic, or fluciclovine PET. The prostate and SV will not be treated with EBRT.
- 6.5.3 The CTV_5040 will include the GTV with 5 mm margin as well as the pelvic lymph nodes as defined by RTOG guidelines. If patients have common iliac involvement or if the treating physician deems it necessary, the para-aortic nodes will be included in the CTV up to the level of the renal vessels. This CTV will be expanded by 0.6 cm to create PTV_5040. This will be treated to 5040 cGy in 28 fractions of 180 cGy.

- 6.5.4 A simultaneous integrated boost (SIB) to the involved nodes will be created. The GTV will receive up to 7000 cGy in 28 fraction of 250 cGy as part of this SIB.
- 6.5.5 Of note, normal tissue tolerances will typically take priority over total dose to the GTV, and PTV_5040. It is encouraged that the target volumes be restricted in areas of overlap with prior the prior RT based on treating physician discretion while ensuring adequate coverage of gross disease. This PTV will be the PTV_high_risk. For example, if the lower obturator nodes received ≥ 50 Gy with the prior radiotherapy plan, then in areas of this nodal region that do not have gross disease treatment can be omitted to avoid overlap between the current field and prior field in the rectum and bladder and femoral heads. If the treating physician and PI feel it is necessary to violate the normal tissue constraints, this is acceptable.

6.5.6 Normal Tissue Constraints:

Minimize areas of overlap with prior radiotherapy, particularly areas of cumulative doses > 80 Gy in the rectum, bladder, and femoral heads.

Bowel space: $V55 < 1$ cc, $V60 < 0.1$ cc.

Rectum: $V70 < 10\%$, Max dose < 7350

Sigmoid: $V70 < 10\%$, Max dose < 7350

Bladder: $V70 < 10\%$, Max dose < 7350

Femoral Heads: $V50 < 10\%$

Guidelines for PTV and GTV coverage (can be violated based on normal tissue goals): $V100 > 95\%$, $V95 > 99\%$

- 6.5.7 Daily CBCT will be performed setting up to the GTV lesions, with priority of coverage of these lesions. Second priority will be set up to the bony anatomy.

7.0 HORMONE THERAPY

Other than androgen deprivation therapy, patients must not receive other cancer-directed therapy (including standard fractionated radiotherapy, chemotherapy, biological therapy, and surgery) while on-study except at disease progression.

Standard institutional practices for neoadjuvant/concurrent and adjuvant short-term (6 months) androgen deprivation hormonal therapy will be used with the salvage

radiotherapy regimen. When possible, radiotherapy will begin approximately 2 months after the start of hormonal therapy. Some patients may have received prior hormonal therapy, but still require 6 months with the trial.

7.1 Anti-Androgen Therapy: Casodex (Bicalutamide)

For further information, consult the package insert.

7.1.1 Timing: Oral anti-androgen therapy will begin approximately within 10 days of the start of the LHRH agonist. It should continue until the completion of radiotherapy.

7.1.2 Bicalutamide is a nonsteroidal antiandrogen, which has no androgenic or progestational properties. The chemical name is propanamide, N-[4-cyano-3(trifluoromethyl)phenyl]- 3- [(4-fluorophenyl)sulphonyl]- 2- hydroxy- 2-methyl, (+,-). Bicalutamide is a racemic mixture with the antiandrogen activity residing exclusively in the (-) or R-enantiomer. Bicalutamide has a long half-life compatible with once-daily dosing.

7.1.3 Supply: Commercially available.

7.1.5 Administration: Bicalutamide is administered orally at a dose of one 50 mg tablet per day. Bicalutamide will begin approximately within (before, same day as, or after) 10 days of the date of the first LHRH agonist administration, and continue until the end of the radiation therapy. Administration will be suspended only if there is an apparent or suspected reaction to the drug. During RT interruptions, bicalutamide will be continued.

7.1.6 Toxicity: Consult the package insert for comprehensive toxicity information. In animal experiments, birth defects (abnormal genitalia, hypospadias) were found in male offspring from female animals dosed with bicalutamide during pregnancy. Although offspring from male animals dosed with bicalutamide did not show any birth defects, patients enrolled in this trial are advised not to cause pregnancy nor donate sperm while receiving protocol therapy or during the first 3 months after cessation of therapy. The use of barrier contraceptives is advised. The most frequent adverse events reported among subjects receiving bicalutamide therapy are breast tenderness, breast swelling, and hot flashes. When bicalutamide 50 mg was given in combination with an LHRH analog, the LHRH analog adverse event profile predominated with a high incidence of hot flashes (53%) and relatively low incidences of gynecomastia (4.7%) and breast pain (3.2%). Other side effects include impotence and loss of libido, fatigue, and rarely, photosensitivity and diarrhea.

7.1.7 Dose Modifications: AST and ALT will be measured pretreatment and during the first week of EBRT. If the AST or ALT rises to $\geq 2x$ the institutional upper limit of normal, bicalutamide must be discontinued.

Elevated AST/ALT values to < 2x the institutional upper limit of normal are subject to dose modifications or discontinuation of anti-androgen at the discretion of the treating physician.

7.2 LHRH Agonist Therapy (leuprolide, goserelin)

For additional information, consult the package inserts.

- 7.3.1 Timing: The first LHRH administration will occur together with the start of anti-androgen treatment ~8 weeks prior to the start of RT. The total duration of LHRH therapy will be 6 months. The total administered duration as well as the specific agent used must be documented.
- 7.3.2 Description: LHRH agonists are long-acting analogs of the native LHRH peptide and are effective at reducing serum testosterone. Analogs approved by the FDA (or by Health Canada for Canadian institutions) can be used in this study.
- 7.3.3 Supply: Commercially available.
- 7.3.4 Storage: LHRH analogs should be stored as directed by the commercial supplier.
- 7.3.5 Administration: LHRH analogs are administered with a variety of techniques, including subcutaneous insertion of a solid plug in the abdominal wall (Zoladex), intramuscular injection (Lupron), subcutaneous injection (Eligard), or insertion of a long-acting cylinder that slowly releases the agent (Viadur). The manufacturer's instructions should be followed.
- 7.3.6 Toxicity: Consult the package insert for comprehensive toxicity information. Class-related toxicity is generally a manifestation of the mechanism of action and related to low testosterone levels. In the majority of patients testosterone levels increase above normal in the first week, declining thereafter to baseline levels or below by the end of the second week of treatment. The most common side effect of LHRH analogs is vasomotor hot flashes; edema, gynecomastia, bone pain, thrombosis, and gastrointestinal disturbances have occurred. Potential exacerbations of signs and symptoms during the first few weeks of treatment is a concern in patients with vertebral metastases and/or urinary obstruction or hematuria which, if aggravated, may lead to neurological problems such as temporary weakness and/or paresthesia of the lower limbs or worsening of urinary symptoms. Other side effects include impotence and loss of libido, weight gain, depression, dizziness, loss of bone density, anemia, increased thirst and urination, unusual taste in the mouth, skin redness or hives, pain at injection site, and muscle mass and strength loss, hair changes, penile length and testicular volume loss, increased cholesterol, hypertension, diabetes exacerbation, emotional lability, nausea, vomiting, and rarely, allergic generalized rash and difficulty breathing.

8.0 STUDY PROCEDURES

8.1 Screening/Baseline Procedures

Assessments performed exclusively to determine eligibility for this study will be done only after obtaining informed consent. Assessments performed for clinical indications (not exclusively to determine study eligibility) may be used for baseline values even if the studies were done before informed consent was obtained.

All screening procedures must be performed within 3 months prior to registration unless otherwise stated. The screening procedures include:

8.1.1 Informed Consent

8.1.2 Medical History

Complete medical, surgical, and oncologic history including previous radiotherapy history.

8.1.3 Demographics

Age, gender, race, ethnicity.

8.1.4 Review subject eligibility criteria

8.1.5 Review previous and concomitant medications

8.1.6 Physical exam

8.1.7 Performance status

ECOG performance status evaluated prior to study entry according to Appendix D.

8.1.8 Adverse event assessment

Baseline adverse events from prior radiotherapy regimen will be assessed. See section 10.0 for adverse event monitoring and reporting.

8.1.9 Tumor assessment

To be performed with at least a PSA, DRE, multi-parametric MRI of the prostate, bone scan and functional imaging (Fluciclovine PET is encouraged).

8.1.10 Baseline quality of life assessment

Documentation of patient's AUA IPSS score, and completion of EPIC-26 instrument; documentation of medication used to treat urinary, bowel, or erectile dysfunction

8.1.11 Labs

AST, ALT, Alkaline Phosphatase, and any labs required for the brachytherapy procedure as part of usual care.

8.2 *Follow-up Procedures*

Patients will be followed as described in Section 8.3.

8.3 *Study Parameters*

	Pre-study	Start of EBRT	Week 4 post-treatment	Month 3 & 6	Month 12	Follow-up Q 6 months*	Time of Biochemical Recurrence
Informed Consent	X						
History and PE, including DRE	X		X	X	X	X	
Medication Assessment	X		X	X	X	X	
Performance Status	X		X	X	X	X	
Toxicity Assessment			X	X	X	X	
PSA	X			X	X	X	
Bone scan	X						X
MP-MRI	X						X¥
PET/CT	X						
IPSS score	X		X	X	X	X	
EPIC-26	X		X	X	X	X	
AST/ALT/ALK PHOS	X	X					

* Until disease progression, death, or follow up period is complete

¥If MP-MRI reveals any suspicious lesions, then biopsy is encouraged.

DRE – Digital Rectal Exam

PE – Physical Exam

MP – Multi-parametric

EBRT – External Beam Radiotherapy

8.4 *Removal of Subjects from Study*

Patients can be taken off the study treatment and/or study at any time at their own request, or they may be withdrawn at the discretion of the investigator for safety, behavioral, or administrative reasons. The reason(s) for discontinuation will be documented and may include:

- 8.4.1 Patient voluntarily withdraws prior to treatment;
- 8.4.2 Patient withdraws consent (termination of treatment and follow-up);
- 8.4.3 Patient is unable to comply with protocol requirements;
- 8.4.4 Patient develops interval co-morbidity that makes continuation in the protocol unsafe;
- 8.4.5 Treating physician(s) judge(s) the study would not be in the patient's best interest;
- 8.4.6 Development of second malignancy (except for basal cell carcinoma or squamous cell carcinoma of the skin) that requires treatment, which would interfere with this study;
- 8.4.7 If a research subject cannot be located to document survival after a period of 2 years; the subject may be considered "lost to follow-up". All attempts to contact the subject during the two years must be documented and approved by the Data Monitoring Committee.

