2.0 STUDY OBJECTIVES

2.1 *Primary Objective*

2.1.1 To determine the incidence of acute grade ≥ 3 radiation-related genitourinary (GU) and gastrointestinal (GI) toxicity of this treatment approach

2.2 *Secondary Objectives*

- 2.2.1 To describe the acute and late toxicity profile with this approach
- 2.2.2 To evaluate disease control efficacy outcomes (biochemical progression-free survival, local control, regional recurrence, cause-specific survival, overall survival, *etc.*)
- 2.2.3 To evaluate patient reported health related quality of life following this treatment approach
- 2.2.4 To describe the dosimetry in patients undergoing this approach

2.3 *Endpoints*

2.3.1 Primary Endpoint:

2.3.1.1 3-month radiation-related grade ≥ 3 GU and GI toxicity as defined by Common Terminology Criteria for Adverse Events (CTCAE) v4.03 (Link available in Appendix A).

2.3.2 Secondary Endpoints:

2.3.2.1 All-grade acute and late toxicity as defined by CTCAE v4.03 criteria (see Appendix A)

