9.0 MEASUREMENT OF EFFECT

9.1 *Antitumor Effect- Solid Tumors*

9.1.1 Definitions:

Evaluable for toxicity: All patients will be evaluable for toxicity immediately following brachytherapy.

Evaluable for disease control assessment: All patients with at least 2 follow-up PSAs will be evaluable for disease control. After brachytherapy, these patients will have their disease status classified according to the definitions stated below.

Biochemical (PSA) recurrence (BR): Based on RTOG Phoenix definition: an increase of the PSA level at least 2 ng/ml greater than the minimum level after therapy (REF: phoenix paper)

All patients with BR should undergo at least MP-MRI of the prostate and bone scan. Biopsy of any suspicious lesions within the prostate gland on MP-MRI is encouraged.

Freedom from Biochemical (PSA) Recurrence (FFBR):

The time to PSA failure will be measured from the date of treatment to the date of a rise by 2 ng/mL or more above the nadir PSA. The time of failure will be the date of the first PSA that is 2 ng/mL or more above the lowest prior post-treatment PSA value. If the rise in PSA to $>$ nadir + 2 occurs during the first 36 months followed by a subsequent non-hormonal induced PSA decrease, patients will **not** be considered PSA failures.

As a benign “spike” or “bounce” in the PSA value has been described in as many as 35% of patients 12-36 months following brachytherapy, intervention for a PSA failure should be based on a positive prostate biopsy at least 24 months post-treatment and/or clinical evidence of distant relapse (i.e., bone scan, CT scan, etc).

Local Failure (LF): This rating will be assigned when there is biopsy-proven disease progression or recurrence at the lesion within the prostate treated with protocol therapy. Histologic criterion for local failure is the presence of prostatic carcinoma upon biopsy more than 2 years after the start of treatment. Residual carcinoma on biopsy should show minimal radiation effect and should be in clinical scenario of increasing PSA.

Local Control (LC): Absence of local failure. This will be assumed in patients with a controlled PSA and for those with PSA failure but no radiographic, clinical, or biopsy-proven disease at the lesion treated with protocol therapy.

Freedom from Local Failure (FFLF): The time to local progression will be measured from the date of treatment to the date of local failure.

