13.5.2 Patient Registration (please refer to Sections 3.0 & 5.0)

Please refer to Sections 3.0 & 5.0 for more extensive instructions. Before a patient can be treated on study, please complete and submit the following

items to confirm patient eligibility and receive a subject registration number:

1. Eligibility CRF.
2. Signed and dated informed consent document.
3. Clinical, laboratory and imaging workup, as well as baseline quality of life assessment

13.6 *Data Submission Guidelines*

Once a subject is confirmed and enrolled to the study, the following CRFs should be submitted to the Radiation Oncology Research Office. Specific timeframes will be defined according to the study parameters table (Section 8.3), but in general, on-study data should be submitted no later than 5 business days after the date of subject registration. Accrual on a trial may be suspended if data is not submitted within 90 days after the data's due date (as it is defined by the protocol)

- 13.6.1 All patient data will be entered into our brachytherapy REDCap database, including baseline information, all follow-up information, including but not limited to disease control parameters as detailed in section 9.0, and patient reported and physician graded toxicity. Additionally, adverse events and survival status will be reported in the database as well.

13.7 *Adherence to the Protocol*

Except for an emergency situation in which proper care for the protection, safety, and well-being of the study patient requires alternative treatment, the study shall be conducted exactly as described in the approved protocol.

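### Toxicity grading is unscheduled at both implants and throughout the 28-fraction EBRT course, so transient non-serious grade 3 events can go ungraded in the primary endpoint and the 2-of-7 stop

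*Combined protocol and SAP*

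**What the plan says.** - **Objective and endpoint.** Section 2.1.1 gives the primary objective: "To determine the incidence of acute grade ≥ 3 radiation-related genitourinary (GU) and gastrointestinal (GI) toxicity of this treatment approach". Section 2.3.1.1 sets the endpoint as "3-month radiation-related grade" 3 or higher GU and GI toxicity under CTCAE v4.03.
- **Treatment.** Section 6.1.1: "Patients will undergo 2 implants with 1 fraction of 12 Gy delivered with each implant". Section 6.5.3 gives EBRT in 28 fractions. Section 6.0 allows brachytherapy before, after or within the EBRT course.
- **Calendar.** In 8.3 the row "Toxicity Assessment" is marked at Week 4 post-treatment, Months 3 and 6, Month 12 and every 6 months afterwards. It is blank at Pre-study and at Start of EBRT. Start of EBRT is the only on-treatment column, and it carries liver enzymes and alkaline phosphatase alone. There is no implant column.
- **Baseline.** Section 8.1.8: "Baseline adverse events from prior radiotherapy regimen will be assessed". Exclusion 3.2.1 bars "Preregistration GI or GU toxicity (for any reason) grade" 3 or higher, which cannot be applied without grading at entry.
- **Evaluability.** Section 9.1.1: "All patients will be evaluable for toxicity immediately following brachytherapy".
- **Decision rules (12.2).** Stop if 2 or more of the first 7 patients have a toxic response. Otherwise accrue to 24 and reject a 33% rate if at least 20 are free of toxicity. The stated type I error is .046, the power 81% at a true rate of 10%, and the early-stopping probability 73%.

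**The concern.** The endpoint is an incidence of acute events, and acute GU/GI effects can arise and settle while radiation is being given or soon after. Section 9.1.1 makes patients evaluable straight after brachytherapy, but the calendar sends nobody to grade them then or at any time during EBRT. Section 13.6 takes its case-report-form timeframes from the same calendar, so following it produces no on-treatment toxicity form.

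The error can run in only one direction. A missed event makes the first stage look safer and the final count look better. Both rules rest on the same count, so neither protects the other. In a re-irradiation study whose main purpose is safety, wrongly concluding that toxicity is acceptable is the more costly mistake.

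**Working it through.** **1. Does another provision schedule on-treatment grading?**
- 10.2 follows an adverse event until it resolves, once it is known. It sets no visits.
- 10.3.1 covers events in patients receiving study treatment and assigns attribution to the treating physician and the principal investigator. 10.3.2 requires CTCAE grading. Neither sets a time at which patients are asked or examined.
- 10.6.1 has the principal investigator notified of serious adverse events within 24 hours of their becoming known. A grade 3 event need not be serious, but it counts toward the endpoint.
- 10.6.2 sends other adverse events to annual routine reporting. 10.7 has the investigator evaluate grade 3 or 4 toxicities. Both act on events already detected.
- 13.6.1 requires physician-graded toxicity and adverse events to be entered in the database, with no on-treatment time point.
- The patient questionnaires are first repeated at Week 4 post-treatment. The symptom score looks back about a month and EPIC-26 mostly 4 weeks. If Week 4 is counted from the last fraction, those windows largely exclude treatment itself.

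Result: what is noticed must be recorded, but nothing schedules the noticing.

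**2. How long is the interval?** Assume five fractions a week and Week 4 counted from the end of EBRT. Then 28/5 = 5.6 weeks, and 5.6 + 4 = 9.6, or about 10 weeks from the first EBRT fraction. Implants outside the EBRT course would lengthen it. If Week 4 is counted from brachytherapy and brachytherapy is given first, the visit could fall during EBRT and the interval would be shorter. The protocol does not settle which applies.

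**3. Reproduce the stated design.** Inputs from 12.2: continue if at most 1 of 7 is toxic; declare acceptable toxicity if at most 24 − 20 = 4 of 24 are toxic. With p the recorded rate:

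P(stop) = 1 − Bin(0; 7, p) − Bin(1; 7, p)

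P(declare acceptable) = Bin(0; 7, p) × P(Bin(17, p) ≤ 4) + Bin(1; 7, p) × P(Bin(17, p) ≤ 3)

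- p = .33: P(stop) = 1 − .0606 − .2090 = .730. P(declare) = .0606 × .2913 + .2090 × .1366 = .0177 + .0285 = .046.
- p = .10: P(declare) = .4783 × .9779 + .3720 × .9174 = .4677 + .3413 = .809.

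The stated .046, 81% and 73% all reproduce; the 73% is the value at a true rate of 33%.

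**4. What if some events are missed?** Let m be the share of patients with a qualifying event whose event goes unrecorded. The recorded rate is then .33 × (1 − m). The documents give no value for m, so the range is an assumption.

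| Missed share m | Recorded rate | P(stop at stage 1) | P(wrongly declare acceptable) |
|---|---|---|---|
| 0 | .330 | .730 | .046 |
| 10% | .297 | .664 | .086 |
| 20% | .264 | .589 | .151 |
| 30% | .231 | .507 | .244 |

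For example, at m = 20%: .1170 × .5204 + .2937 × .3055 = .0609 + .0897 = .151.

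**5. Baseline.** Section 8.1.8 requires the assessment, the introduction to 8.1 places screening procedures within 3 months before registration, and 3.2.1 depends on the result. The blank Pre-study cell in 8.3 conflicts with all three.

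**The case against.** The strongest reply is that section 10 already covers the treatment period. Any untoward occurrence in a patient on study treatment is an adverse event, must be graded and attributed, and must reach the database; the investigator's review of grade 3 or 4 toxicities is limited neither to serious events nor to calendar visits. Patients attend repeatedly for EBRT and are in the department for each implant, and the Week 4 visit includes history, examination and medication review. No clause restricts the endpoint to findings at scheduled visits.

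This stands, and it limits the point. A reader of table 8.3 alone might infer that on-treatment events are not collected, or that the endpoint counts only what is still present or remembered at Week 4. The documents do not support either inference. A reader might also infer from the blank Pre-study cell that no baseline toxicity is taken; 8.1.8 and 3.2.1 show otherwise, so that cell is an inconsistency between table and text.

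It is equally fair to say that the missed shares are hypothetical and that a gap of about 10 weeks depends on an undefined anchor and an assumed five-day week.

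The reply does not supply a time at which someone is required to ask about and grade GU/GI toxicity between the first fraction and Week 4. For a transient, non-serious grade 3 event, capture rests on unscheduled noticing or later recall.

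**Conclusion.** The point holds in limited form. Capture of acute GU/GI toxicity during radiation is required in principle but unscheduled in practice, and the first scheduled grading is tied to an undefined date. The events at risk are mainly transient, non-serious grade 3 ones. Any shortfall weakens both the stage-1 stop and the final test in the anti-conservative direction.

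The size cannot be estimated from the documents. Conditional on a true rate of 33% and on events being missed independently across patients, losing 10% nearly doubles the false-acceptance probability (.046 to .086), and losing 30% brings it to .244 with stage-1 stopping close to an even chance (.507). With complete capture the stated operating characteristics are correct, so the design arithmetic needs no change. The Pre-study cell is a separate, smaller inconsistency.

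**What to change.** 1. In 8.3, mark toxicity assessment at Pre-study, to agree with 8.1.8.
2. Add CTCAE v4.03 GU/GI grading at regular on-treatment EBRT attendances (for example weekly), on each implant day, and at the next scheduled attendance after each implant. The last of these should be a named visit, because no EBRT attendance follows if the implants come last.
3. Define the primary endpoint as the worst radiation-related GU/GI grade from the first radiation fraction to Month 3, in the same words in 2.3.1.1, 12.1 and 12.2.
4. State the date from which Week 4 and Month 3 are counted, for example the last radiation fraction, whichever modality comes last.

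The cost is an edit to the calendar and additional case-report-form pages. Grading on EBRT and implant days uses attendances that already take place. The observed toxicity rate may be higher than under the present calendar, because events that would otherwise go ungraded are counted. No change to treatment is involved.
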